10.2. Patient consent

10.2.1. Subjects who are alive and visit the study site

The investigator explains participation to patients using the reviewed and approved patient information sheet. An informed consent form is then used to obtain written consent from fully informed patients. The investigator explains that participation in the research is completely voluntary and that subjects are free to withdraw their consent at any time, even after providing consent form. In addition, the attending physician have to take necessary measures to ensure that subjects' rights to self-determination and treatment choice are not limited and that they would not be penalized for refusing or withdrawing consent from participation in the study. The informed consent form will then be revised after institutional review board (IRB)/independent ethics committee grants approval, and written consent will be obtained from each subject.

- Information to be provided to subjects
 - 1) Title of the study and the fact that approval of the chief executive of the study site has been given concerning its implementation.
 - 2) Names of the study site and the principal investigator (including names of the collaborative study site(s) and principal investigators of such collaborative study site(s), when the study is conducted collaboratively with other study site(s));
 - 3) Objectives and significance of the study;
 - 4) Method and time period of the study (including purpose of utilization of specimens or information acquired from the subject);
 - 5) Reasons why asked to be enrolled in the study;
 - 6) Burdens to be caused on the subjects and predictable risks and benefits;
 - 7) The fact that subjects, etc. may withdraw their consent at any time even after they have given consent with regard to the study being commenced or continued (when it can be difficult to take measures that follow the withdrawal made by the study subject, etc., a statement to that effect and the reason for the difficulty).
 - 8) The fact that the refusal or withdrawal of consent by a study subject, etc., with regard to the study is to be commenced or continued does not cause any disadvantage to such subject, etc.
 - 9) Means to make information on the study public;

PFIZER CONFIDENTIAL

- 10) The fact that subjects, etc. can request and obtain or read the study protocol and documents concerning method of the study, to the extent it does not interfere the protection of personal information, etc. of other subjects, etc. or the originality of the study, as well as the procedure to obtain or read such protocols and documents;
- 11) Handling of personal information, etc. (including process of anonymization, when anonymization is conducted);
- 12) Means for storage and disposal of specimens and information;
- 13) Status of study-related conflicts of interest of the study site, such as study fund resources as well as study-related conflicts of interest of each investigator, such as his/her individual income.
- 14) Response to consultation, etc. made by subjects, etc. and other individuals concerned.
- 15) When the study involves any financial expenditure on or remuneration for the subject, etc., a statement to that effect and details of such;
- 16) When the study involves any invasiveness, whether compensation will be offered for study-related injury and details of such compensation.
- 17) With respect to specimens and information acquired from the subject, when any of those may be utilized or provided to other study site(s) for future study that is not identified at the time of obtaining consent from the study subject, etc., a statement to that effect and the contents of utilization assumed at the time of obtaining consent; or
- 18) When the study involves any invasiveness (not including minor invasiveness) and intervention, the fact that the monitor(s), the auditor(s), and the ethical review committee will be granted direct access to the specimens and information acquired from the subjects to the extent necessary, without violating the confidentiality of the subjects.

10.2.2. Subjects who are alive and had been transferred to another hospital

It is not always necessary to obtain written informed consent when existing information is provided to another hospital, but the individual providing existing information must obtain oral informed consent.

10.2.3. Subjects who have died

Because the study is retrospective, informed consent could not be obtained from subjects who had died or had failed to visit the study site. Instead of informed consent, the investigator must provide the legal representatives of the subjects an opportunity to refuse participation in the study. The following information must be made public:

- 1) purpose for which the information will be used;
- 2) item of collected information;

- 3) person responsible for information management;
- 4) organization that will be provided information;
- 5) how to manage refusal—if the subject refuses participation in the study, their data cannot be used.

10.3. Patient withdrawal

10.3.1. Subjects who are alive and visit the study site, or subjects who are alive and had been transferred to another hospital

During the course of this study, the subject can withdraw his/her consent at any time. In any circumstance, every effort should be made to document patient outcomes, if possible. If the patient withdraws from the study and withdraws consent for disclosure of future information, no further evaluations should be performed and no additional data should be collected. The sponsor may retain and continue to use any data collected before withdrawal of consent.

10.3.2. Subjects who have been died

When the legal representatives of subjects refuse to participate in the study during the study period, all of their data must be excluded from the analysis dataset. If the results of this study are disclosed on paper or conference at the time of refusal, the subject's data cannot be excluded.

10.4. Institutional review board (IRB)/Independent ethics committee (IEC)

There must be prospective approval of the study protocol, protocol amendments, and other relevant documents (e.g., informed consent forms if applicable) from the relevant IRBs/IECs. All correspondence with the IRB/IEC must be retained. Copies of IRB/IEC approvals must be forwarded to Pfizer.

10.5. Ethical conduct of the study

The study will be conducted in accordance with legal and regulatory requirements, as well as with scientific purpose, value and rigor and follow generally accepted research practices described in the Ethical Guidelines for Medical and Health Research Involving Human Subjects issued by the Ministry of Health, Labor and Welfare (MHLW).

10.6. Predictable risks and benefits

10.6.1. Risk

The subjects' data will be collected retrospectively in this study, so there is no added risk to any individual subject.

10.6.2. Benefits

For individual subjects, there is no particular benefit because the study had a retrospective study design.

10.7. Conflicts of interest

This study will be performed with funding from Pfizer Inc. The investigators will review any conflicts of interests that may affect the planning of this study or the interpretation of results by the IRB/IEC or the Conflicts of Interest Committee, according to the regulations of the study site. When the results of the study are published, accurate information will be disclosed by self-reporting in compliance with the guidelines of the academic society or journal used for publishing the results of the study.

10.8. Registration and publication of study

Prior to implementation, this study and a summary were registered in the public database of UMIN-CTR and clinicaltrials.gov. Registered content will be properly updated without delay.

10.9. Secondary use of specimens and information obtained from subjects

The data obtained from this study may be used in other studies with different purposes. Such use will only be possible if another protocol is developed and approved by the IRB/IEC.

10.10. Responding to consultations from subjects and other related parties

The principal investigator will set up a helpline for handling consultations about this study from subjects and other related parties. Information about each site helpline is included in the informed consent form and document related to opt-out.

11. MANAGEMENT AND REPORTING OF ADVERSE EVENTS/ADVERSE REACTIONS

This study protocol requires human review of patient-level unstructured data; unstructured data refer to verbatim medical data, including text-based descriptions and visual depictions of medical information, such as medical records, images of physician notes, neurological scans, X-rays, or narrative fields in a database. The reviewer is obligated to report adverse events (AEs) with explicit attribution to any Pfizer drug that appear in the reviewed information (defined per the patient population and study period specified in the protocol). Explicit attribution is not inferred by a temporal relationship between drug administration and an AE, but must be based on a definite statement of causality by a healthcare provider linking drug administration to the AE.

The requirements for reporting safety events on the non-interventional study (NIS) adverse event monitoring (AEM) Report Form to Pfizer Safety are as follows:

- All serious and non-serious AEs with explicit attribution to any Pfizer drug that appear in the reviewed information must be recorded on the <data collection tool (e.g., chart abstraction form)> and reported, within 24 hours of awareness, to Pfizer Safety using the NIS AEM Report Form.

- Scenarios involving drug exposure, including exposure during pregnancy, exposure during breast feeding, medication error, overdose, misuse, extravasation, lack of efficacy, and occupational exposure associated with the use of a Pfizer product must be reported, within 24 hours of awareness, to Pfizer Safety using the NIS AEM Report Form.

For these AEs with an explicit attribution or scenarios involving exposure to a Pfizer product, the safety information identified in the unstructured data reviewed is captured in the Event Narrative section of the report form, and constitutes all clinical information known regarding these AEs. No follow-up on related AEs will be conducted.

“All the demographic fields on the NIS AEM Report Form may not necessarily be completed, as the form designates, since not all elements will be available due to privacy concerns with the use of secondary data sources. While not all demographic fields will be completed, at the very least, at least one patient identifier (e.g., gender, age as captured in the narrative field of the form) will be reported on the NIS AEM Report Form, thus allowing the report to be considered a valid one in accordance with pharmacovigilance legislation. All identifiers will be limited to generalities, such as the statement “A 35-year-old female...” or “An elderly male...” Other identifiers will have been removed.

Additionally, the onset/start dates and stop dates for “Illness”, “Study Drug”, and “Drug Name” may be documented in month/year (mmm/yyyy) format rather than identifying the actual date of occurrence within the month /year of occurrence in the day/month/year (DD/MMM/YYYY) format.”>

All research staff members must complete the following Pfizer training requirements:

“YRR Training for Vendors Working on Pfizer Studies (excluding interventional clinical studies and non-interventional primary data collection studies with sites/investigators)”.

These trainings must be completed by research staff members prior to the start of data collection. All trainings include a “Confirmation of Training Certificate” (for signature by the trainee) as a record of completion of the training, which must be kept in a retrievable format. Copies of all signed training certificates must be provided to Pfizer.

Re-training must be completed on an annual basis using the most current Your Reporting Responsibilities training materials.

12. PLANS FOR DISSEMINATING AND COMMUNICATING STUDY RESULTS

In the event of any prohibition or restriction imposed (e.g., clinical hold) by an applicable competent authority in any area of the world, or if the investigator is aware of any new information which might influence the evaluation of the benefits and risks of a Pfizer product, Pfizer should be informed immediately.

The results of this study are not part of any regulatory submission. The results of this study will be submitted for abstracts and publications. The final output will be filed in Pfizer's Global Document Management System upon final study completion.

14. LIST OF TABLES

Table 1 Key variables of interest and data collection timepoints.

15. LIST OF FIGURES

Figure 1 Study flow for patients who are alive and visit the study site

Figure 2 Study flow for patients who have died

ANNEX 1. LIST OF STAND ALONE DOCUMENTS

Number	Document reference number	Date	Title

ANNEX 2. ENCEPP CHECKLIST FOR STUDY PROTOCOLS

Not applicable

ANNEX 3. ADDITIONAL INFORMATION

Annex 3A. Description of the Eastern Cooperative Oncology Group (ECOG) Performance Status.

[figure not shown]
Grade	Description
Grade 0	Fully active, able to carry on all pre-disease performance without restriction.
Grade 1	Restricted in physically strenuous activity but ambulatory and able to carry out work of a light or sedentary nature, e.g., light house work, office work.
Grade 2	Ambulatory and capable of all selfcare but unable to carry out any work activities; up and about more than 50% of waking hours.
Grade 3	Capable of only limited selfcare; confined to bed or chair more than 50% of waking hours.
Grade 4	Completely disabled; cannot carry on any selfcare; totally confined to bed or chair.
Grade 5	Dead

Reference: Oken M, Creech R, Tormey D, et al. Toxicity and response criteria of the Eastern Cooperative Oncology Group. Am J Clin Oncol. 1982; 5:649-655.

Annex 3B. Definitions for Tumor, Node and Metastasis (TNM) descriptors.

Grade	T (primary tumor)
T0	No primary tumor
Tis	Carcinoma in situ (squamous or adenocarcinoma)
T1	Tumor \leq 3cm
T1mi	Minimally invasive adenocarcinoma
T1a	Superficial spreading tumor in central airways
T1a	Tumor \leq 1cm
T1b	Tumor >1 but \leq 2cm
T1c	Tumor >2 but \leq 3cm
T2	Tumor >3 but \leq 5cm or tumor involving: visceral pleura, main bronchus (not carina), atelectasis to hilum
T2a	Tumor >3 but \leq 4cm
T2b	Tumor >4 but \leq 5cm

PFIZER CONFIDENTIAL

T3	Tumor >5 but ≤7cm or invading chest wall, pericardium, phrenic nerve; or separate tumor nodule(s) in the same lobe
T4	Tumor >7cm or tumor invading: mediastinum, diaphragm, heart, great vessels, recurrent laryngeal nerve, carina, trachea, esophagus, spine; or tumor nodule(s) in a different ipsilateral lobe
	N (regional lymph nodes)
N0	No regional node metastasis
N1	Metastasis in ipsilateral pulmonary or hilar nodes
N2	Metastasis in ipsilateral mediastinal or subcarinal nodes
N3	Metastasis in contralateral mediastinal, hilar, or supraclavicular nodes
	M (distant metastasis)
M0	No distant metastasis
M1a	Malignant pleural or pericardial effusion or pleural or pericardial nodules or separate tumor nodule(s) in a contralateral lobe
M1b	Single extrathoracic metastasis
M1c	Multiple extrathoracic metastases (1 or >1 organ)

Reference: Rami-Porta R, Asamura H, Travis WD, Rusch VW. Lung cancer: Major changes in the American Joint Committee on Cancer eighth edition cancer staging manual. CA Cancer J Clin. 2017;67(2):138-155.

1 AMENDMENTS FROM PREVIOUS VERSIONS

This statistical analysis plan (SAP) for Study B7461038 is based on the protocol dated 15APR2021.

Table 1 Summary of Changes

Version/Date	Associated Protocol Amendment	Rationale	Specific Changes
1 08APR2021	Version 1 19MAR2021	NA	NA
2 08SEP2021	Version 2 15APR2021	Incorporate amended content of the protocol	
 • Add the observation period in Section 2.1 • Clarify that the time to failure of subsequent other treatment will be summarized by each line of lorlatinib therapy in Section 7.2.1
3 12MAY2022	Version 2 15APR2021	Add the ad-hoc analysis following advisory board meeting results	
 • Add time to last treatment failure in Section 5.1.4. • Add the analysis method for time to last treatment failure in Section 7.

2 INTRODUCTION

This SAP provides the detailed methodology for summary and statistical analyses of the data collected in Study B7461038. This document may modify the plans outlined in the protocol; however, any major modifications of the primary endpoint definition or its analysis will also be reflected in a protocol amendment.

2.1 STUDY DESIGN

This study is a post-approval, company-sponsored, observational study and a multicenter, non-interventional, retrospective, chart review of patients with anaplastic lymphoma kinase (ALK) positive (+) non-small cell lung cancer (NSCLC) patients treated using lorlatinib as the second-line or later therapy in Japan after failure of alectinib treatment as the first-line therapy from 20th November 2018.

All decisions regarding clinical management and treatment of participating patients were made by an investigator as a part of standard care in real-world clinical setting and were not contingent upon patient's participation in the study. Data will be collected if available per study site. Patients in this study are those who started treatment with lorlatinib from 1st May 2019 to 31st December 2020 in clinical practice.

The observation period will be from the start date of alectinib to 15th October 2021.

2.1.1 Study Population

The study population includes Japanese patients with *ALK*⁺ NSCLC who received lorlatinib as the second-line or later therapy after failure of alectinib treatment as the first-line therapy from 20th November 2018.

PFIZER CONFIDENTIAL

The expected number of patients will be approximately 50 patients treated with lorlatinib in total. The number of patients who received lorlatinib as the second-line therapy will be 30 patients, but this should be considered flexible.

2.1.2 Data Source

As this is a retrospective study, all data will be collected from medical records at the participating study site.

2.1.3 Treatment/Cohort Labels

Patients receiving lorlatinib as the second-line and the third-line therapy may be labeled, respectively, “2L” and “3L” for the purpose of reporting if necessary.

2.2 STUDY OBJECTIVES

The primary objective is to describe the demographic characteristics of patients with *ALK*⁺ NSCLC patients treated with lorlatinib as the second-line or later therapy after failure of alectinib as the first-line therapy in a real-world clinical setting, clinical usage and observed effectiveness of lorlatinib.

The secondary objectives are as follows:

- To describe treatments received including alectinib as the first-line therapy prior to lorlatinib
- To describe treatment pattern after lorlatinib as the second-line or later therapy

3 HYPOTHESES AND DECISION RULES

3.1 STATISTICAL HYPOTHESES

Null and alternative hypotheses in variable selections described in Section [7.2.1](#) are as follows:

H_0 : a regression parameter related to an interesting variable is zero, and

H_1 : a regression parameter related to an interesting variable is not zero.

3.2 STATISTICAL DECISION RULES

[figure not shown]
Two-sided 5% significance level will be used in variable selections described in Section [7.2.1](#).

4 ANALYSIS SETS/POPULATIONS

4.1 FULL ANALYSIS SET

A full analysis set (FAS) will consist of patients who meet the inclusion criteria and do not meet the exclusion criteria.

PFIZER CONFIDENTIAL

INCLUSION CRITERIA

Patients must meet all of the following inclusion criteria to be eligible for inclusion in the study:

1. Histologically or cytologically confirmed NSCLC, with any TNM stage.
2. Confirmed *ALK* gene rearrangement by any validated tests.
3. Confirmed the treatment with alectinib in the first-line setting as systemic therapy in a medical record.
4. Confirmed the start of treatment with lorlatinib as the second-line or later therapy from 1st May 2019 to 31st December 2020.
5. Availability of clinical information from a medical record.
6. Evidence of a personally signed and dated informed consent document indicating that the patient (or a legally acceptable representative) has been informed of all pertinent aspects of the study.
 - (1) Written consent is not required for patients who were transferred to a hospital, and registration with verbal consent is acceptable.
 - (2) Opt-out enrollment is allowed for patients who have already died.

EXCLUSION CRITERIA

Patients meeting the criterion below will not be included in the study:

1. Participating on any clinical trials of which final results has not yet been reported during the study period.

4.2 SUBGROUPS

A subgroup analysis will be considered, including but not limited to subgroup by the line of therapy with regard to lorlatinib.

5 ENDPOINTS AND COVARIATES**5.1 EFFICACY/EFFECTIVENESS ENDPOINTS****5.1.1 Time to Treatment Failure**

Time to treatment failure (TTF) is the time from the first date of interest treatment (either alectinib or lorlatinib) to the date of any-cause treatment discontinuation including disease progression, treatment toxicity and death.

5.1.2 Combined TTF

Combined TTF is defined as sum of the time from the first date of alectinib to the date of any-cause alectinib discontinuation, the time from the first date of lorlatinib to the date of lorlatinib discontinuation and the time from the first date of the other subsequent treatment to the date of other subsequent treatment discontinuation.

5.1.3 Objective Response

Objective response (OR) based on an investigator assessment is defined as complete response (CR) or partial response (PR) according to Response Evaluation Criteria in Solid Tumors (RECIST) v1.1 from the first date of interest treatment (either alectinib or lorlatinib) until the date of treatment discontinuation. Repeat assessments were not required to confirm CR and PR due to a nature of real-world clinical setting.

5.1.4 Time to Last Treatment Failure

Time to last treatment failure (TLTF) is the time from the first date of alectinib to the date of any-cause treatment discontinuation including disease progression, treatment toxicity and death in the last treatment.

5.2 SAFETY ENDPOINTS

There are no safety endpoints in this study.

[figure not shown]
5.3 OTHER ENDPOINTS

5.3.1 Baseline Characteristics

The following patient characteristics at baseline (the first date of alectinib treatment) and/or the first date of lorlatinib treatment will be collected.

- Age (continuous and categorical [<65 years, ≥ 65 years])
- Sex
- Weight
- Height
- Body mass index (BMI) (continuous and categorical [<18.5 kg/m², $18.5 - <25$ kg/m², ≥ 25 kg/m²])
- Eastern Cooperative Oncology Group performance status (ECOG PS)
- Histological type
- Number and site of metastases

PFIZER CONFIDENTIAL

- Complications/medical history (related to history of treatment for *ALK*+ NSCLC)
- Smoking history
- Brinkman index
- ALK test result including ALK testing method and the date of test result/diagnosis
- Number of treatment regimens administered to the target disease prior to the start of lorlatinib treatment

5.3.2 Reason for Discontinuation

Reason for discontinuation of each line will be collected.

5.4 COVARIATES

Potential covariates are, but not limited to, the followings:

- baseline characteristics, and
- reason for discontinuation of lorlatinib treatment.

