9.7.1. Analysis Methods

Characteristics, treatment patterns and outcomes of ALK+ NSCLC patients treated with lorlatinib will be described in SAP .

Continuous variables will be summarized using n, means, standard deviations, medians, IQRs, minimums and maximums. Categorical variables will be summarized using frequencies (counts) and percentages. For the time-to-event endpoints, e.g. TTF, the Kaplan-Meier estimates (product-limit estimates) will be presented together with a summary of associated statistics including the median TTF with 2-sided 95% CIs using Brookmeyer and Crowley method. Censoring rule is shown in Section 9.1.3.1. These endpoint will also be displayed graphically.

Exploratory analyses using Cox proportional hazards model may be performed to examine the association between time-to-event outcomes and independent variables such as baseline patient, disease characteristics (e.g. age, sex, line of lorlatinib therapy, ECOG performance status, CNS metastasis, etc), and the reason for discontinuation of lorlatinib.

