6 HANDLING OF MISSING VALUES

No imputation for missing values will be performed.

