7.1 STATISTICAL METHODS

Continuous variables will be summarized using the number of patients, mean, standard deviation (SD), interquartile range (IQR), minimum, median and maximum. Categorical variables will be summarized using the frequency and percentage. Time-to-event endpoint will be summarized using the Kaplan-Meier method. A confidence interval (CI) of a specific percentile will be derived by the Brookmeyer and Crowley method. A CI of survival probability will be estimated using Greenwood's formula. Cox proportional hazards model may be performed to examine the association between time-to-event endpoint and covariates if data allows.

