7.2 STATISTICAL ANALYSES

7.2.1 Time to Treatment Failure

TTF will be summarized using the Kaplan-Meier method with the Kaplan-Meier plot. Percentiles of survival curve (25%, median and 75%) with their 2-sided 95% CIs will be estimated. Yearly rates with their 2-sided 95% CI will also be provided. If patients

continue a treatment at the date of data entry, TTF will be censored at the available last date of treatment or the study end period.

TTF will be evaluated by each treatment below:

- TTF of alectinib as the first-line therapy,
- TTF of lorlatinib as the second-line therapy,
- TTF of lorlatinib as the third-line or later therapy,
- TTF of lorlatinib across the line of therapy, and
- TTF of subsequent other treatment (e.g., chemotherapy and other TKIs) by each line of lorlatinib therapy

If data allows, Cox proportional hazards model may be performed. Variable selection in Cox proportional hazard model may be performed. Candidates for covariate will be selected by an univariate selection at first. If more than 2 variables are selected in the univariate selection, a stepwise selection will be performed using candidates for covariate after the univariate selection.

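### Reason for stopping lorlatinib is a candidate Cox covariate with no limit on the outcome; in a model for lorlatinib TTF it is the event type and can bias the other hazard ratios

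*SAP*

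**What the plan says.** SAP 5.4 names two kinds of potential covariate: baseline characteristics and "reason for discontinuation of lorlatinib treatment". Protocol 9.7.1 lists the same item at the end of its examples for the exploratory Cox model: "ECOG performance status, CNS metastasis, etc), and the reason for discontinuation of lorlatinib". Neither place ties it to an outcome.

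SAP 7.1 is equally general: "Cox proportional hazards model may be performed to examine the association between time-to-event endpoint and covariates if data allows". SAP 7.2.1 then plans the Cox model and variable selection in the section that analyses TTF of alectinib, of lorlatinib (second line, third line or later, and all lines together) and of other therapy. On selection it says: "Candidates for covariate will be selected by an univariate selection at first", with a stepwise step if more than two variables pass. SAP 3.2 sets the threshold: "Two-sided 5% significance level will be used in variable selections described in Section" 7.2.1. The test statistic is not named.

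Under SAP 5.1.1, TTF runs "to the date of any-cause treatment discontinuation including disease progression, treatment toxicity and death". SAP 7.2.1 adds that if patients "continue a treatment at the date of data entry, TTF will be censored". SAP 6 says: "No imputation for missing values will be performed". SAP 7 puts all analyses on the full analysis set. No text says how the reason is coded for a patient who has not stopped lorlatinib.

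**The concern.** A Cox covariate should be known at time zero or be handled as time-dependent. For lorlatinib TTF the reason for stopping is neither. It comes into being with the event and describes what kind of event it was. Censored patients have no value, and each obvious way to fill the gap lets the outcome define the covariate:

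- If ongoing patients are dropped, the model is conditioned on the event having occurred, and it no longer uses the full analysis set.
- A separate level for ongoing patients contains no events by construction.
- A yes/no flag (progression or toxicity) can be yes only for patients with an event.

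At stake are the adjusted hazard ratios for factors such as ECOG PS, CNS metastasis and line of lorlatinib, and any association reported for the reason itself.

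The reason also arises after time zero for alectinib TTF and for therapy given before lorlatinib. The same is true of Combined TTF and time to last treatment failure, but those two are reached only through the general wording of SAP 7.1, since SAP 7.2.2 and 7.2.4 plan Kaplan-Meier summaries alone. The reason is known at time zero only for therapy started after lorlatinib has stopped.

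**Working it through.** The documents give no figure to reproduce: there is no event count, and protocol 9.5 declines a power calculation. The check is therefore of mechanism and possible size.

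**Inputs from the documents.** Lorlatinib starts run from 1 May 2019 to 31 December 2020 and observation ends 15 October 2021, so potential follow-up is 288 to 898 days, or 9.46 to 29.50 months. About 50 patients are expected. The selection level is two-sided 5%. A median of 5.5 months is lorlatinib PFS after one second-generation ALK-TKI (protocol section 7), used as a proxy for TTF.

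**Assumptions.** Exponential TTF; uniform starts; a binary factor in 30% of patients with true HR 2.0; reference-group median m of 5.5, 12 or 20 months (the last two assumed); reasons assigned at random, 25% toxicity and 75% progression, so the reason carries no information.

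**1. Share censored.** With S(m,r) the mean of exp(−r·ln2·t/m) over t uniform on 9.46 to 29.50, the share is 0.7·S(m,1) + 0.3·S(m,2).
- m = 5.5: 0.7×0.1105 + 0.3×0.0181 = 0.083
- m = 12: 0.7×0.343 + 0.3×0.131 = 0.279
- m = 20: 0.7×0.519 + 0.3×0.281 = 0.448

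Of 50 patients, about 4/14/22 are ongoing and 46/36/28 have events.

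**2. Why dropping ongoing patients attenuates.** For one fixed follow-up c and reference hazard λ = ln2/m, the hazard at t among patients who fail before c is λ/(1 − exp(−λ(c−t))). For a true HR of 2 the ratio becomes 2/(1 + exp(−λ(c−t))). At c = 19.5 months (mid-range) it starts at 2/1.086 = 1.84, 2/1.324 = 1.51 and 2/1.509 = 1.33 for the three medians, and falls to 1 as t approaches c. A separate ongoing level gives the same factor HR, because its fitted hazard goes to zero and those patients leave the risk sets.

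**3. Large-sample Cox fits** (four runs of 600,000; Monte Carlo SE of log HR at most 0.004):

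| Model for lorlatinib TTF | m = 5.5 | m = 12 | m = 20 |
|---|---|---|---|
| Factor HR, reason left out | 2.00 | 2.00 | 2.00 |
| Factor HR, ongoing dropped or own level | 1.71 | 1.38 | 1.23 |
| Factor HR, progression yes/no | 1.88 | 1.60 | 1.44 |
| Factor HR, toxicity yes/no | 1.98 | 1.90 | 1.84 |
| Progression flag's own HR (uninformative) | 1.98 | 4.65 | 8.41 |
| Toxicity flag's own HR (uninformative) | 1.31 | 2.08 | 3.10 |

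**4. Scale against noise at n = 50.** With ongoing patients dropped, the log-HR shift is ln(2/1.71) = 0.16, ln(2/1.38) = 0.37 and ln(2/1.23) = 0.49. A rough standard error for the full model, 1/√(events×0.3×0.7), is 0.32, 0.36 and 0.41. The shift is about half a standard error at the document-anchored median and about one at the longer medians.

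**5. How often an uninformative reason passes the 5% univariate screen, n = 50** (ranges are across simulation runs):

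| Coding | m = 5.5 | m = 12 | m = 20 |
|---|---|---|---|
| Progression yes/no | 51–52% | 99% | 100% |
| Toxicity yes/no | 12–13% | 51–53% | 79–81% |
| Ongoing dropped | 6–7% | 7% | 7–8% |
| Ongoing level, score test | 87–89% | 100% | 100% |
| Ongoing level, Wald test | about 1–2% | about 1–2% | about 1–2% |

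The last two rows differ because a level without events is complete separation: the coefficient runs to minus infinity and the Wald statistic fails.

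**6. Sensitivity.**
- No censoring and constant cause-specific hazards: the HR is 2.01 with and without the reason, so no bias.
- A second set-up (factor in half of patients, toxicity 30% of the hazard, medians 5.5/9/14), ongoing dropped: 2.0 becomes 1.72/1.49/1.28. If toxicity stops come early (Weibull shape 0.5), it becomes 1.58/1.43/1.28, and the reason passes the screen in 43–54% of datasets at n = 50.
- A factor with no effect stayed near 1 (0.97 to 1.02) when unrelated to start date. If its prevalence is assumed to be 15% in early and 45% in late starters, 1.0 becomes 1.14/1.23/1.27 in the first set-up with ongoing dropped; with the reverse pattern it becomes 0.89/0.84/0.82.

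**The case against.** The strongest reply is that nothing here commits the sponsor to an invalid model. The Cox work is optional and exploratory, the study is descriptive with no hypothesis to test, and the covariate is only a potential one. SAP 7.2.1 also lists TTF of other subsequent treatment, where the reason is a legitimate baseline variable, so the authors may simply have left the restriction unsaid. All of that is fair, and it keeps the matter to a recommended clarification. It does not remove the gap: neither document states the restriction, and the same section offers the same selection procedure for lorlatinib TTF.

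The size is also open to challenge. Only the 5.5-month median comes from the documents, and there the shift is about half a standard error. A toxicity flag barely moves the factor HR. SAP 6 points most naturally to dropping ongoing patients, and with that coding an uninformative reason passes the screen at close to the nominal rate, so in the base case the larger attenuation would seldom arise through the screen. This stands for the base case; it weakens if the reason is related to time, as when toxicity stops come early. The null-factor bias rests on a start-date link that no passage suggests.

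A reader might go further and infer that the 5% screen will generally pick up an ongoing level. The documents do not support that, because they name no test, and a score test and a Wald test give opposite answers.

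**Conclusion.** The point holds in conditional form. Because the covariate has no outcome restriction, an optional exploratory model for lorlatinib TTF may contain its own event type, and such a model can give biased hazard ratios for other factors. With starts up to 31 December 2020 and a 15 October 2021 cut-off, some ongoing patients are to be expected, so the no-censoring exception is unlikely to apply exactly. Under the stated assumptions a true 2.0 becomes anything from nearly 2.0 (toxicity flag, short TTF) to about 1.2 (ongoing dropped or own level, long TTF).

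Two stronger readings should be resisted. One is that any model with this term is biased: the bias is small with a toxicity flag and absent without censoring when cause-specific hazards are constant. The other is that the study's TTF results are compromised: Kaplan-Meier summaries, univariate screens of the other covariates and models without the term are untouched. For alectinib TTF, therapy before lorlatinib, Combined TTF and time to last treatment failure, the timing objection applies but the bias was not computed. The documents do not say whether any such model has been run.

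**What to change.** In SAP 5.4 and 7.2.1:

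- State that reason for lorlatinib discontinuation may be a covariate only for TTF of therapy started after lorlatinib, timed from the start of that therapy.
- Exclude it as a candidate for every other time-to-event outcome: lorlatinib TTF, alectinib TTF, TTF of therapy given before lorlatinib, Combined TTF and time to last treatment failure.
- State that this supersedes the unrestricted wording in protocol 9.7.1. Protocol 9.7 lets the SAP modify the plan and asks for an amendment only for major changes to primary endpoint definitions or their analyses. The TTF definition and its Kaplan-Meier analysis do not change.
- Refit without the term any affected model already run.

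If the reasons for stopping lorlatinib are of interest, they can be described with Aalen-Johansen cumulative incidence by reason; this is optional.

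The cost is a short SAP edit and possibly a refit, with no new data and no protocol amendment.
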